5–10 times more potent and enhances its distribution to cerebral tissues, making for easier titration.⁽⁹⁾ The t_{1/2} Ke0 (transfer life from plasma to effect site) is 1.6hr – 4 hr for M, compared to 18-38 min for HM.^(9,10) It is observed that health care providers may be willing to provide higher dose of HM compared to M in EMU, as its actual quantity of drug is much smaller and therefore appears to cause less concern.^(12, 13) Our literature review showed that there are no previous studies comparing these 2 medications in AS patients. The lone systematic review compared various acute and chronic pain studies, in various routes of drug administration.⁽⁹⁾ Of the 11 studies identified; only 4 were done in acute pain settings.⁽¹³⁻¹⁶⁾ Two of them were done by the same author in ER settings. Chang et al noted that HM reduced the mean pain scores by 1.3 units [95% CI= (-2.2 to -0.5)] compared to M in 198 adults treated in ER.^(12,13). However it did not show much difference in geriatric population.¹⁴ In perioperative settings, Hong et al studied the difference in nausea between the 2 medications in 50 patients using PCA and found no difference.⁽¹⁵⁾ Rapp et al studied various effects between the 2 medications in 61 surgical patients using PCA. There is not much clarity about their primary outcome; however they found the effects to be similar.⁽¹⁶⁾ Both these studies had smaller sample sizes. The meta-analysis performed demonstrated that the HM does provide better analgesia than M, with a small effect size; Cohen's d=0.266 (p=0.012).⁽⁹⁾ Looked at acute pain alone it was statistically significant (p=0.006), compared to chronic pain (p=0.889). It was noted that that there is a definite lack of comparative studies between them in surgical settings.

Patients Symptoms after Discharge

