At the end of 2 hours or after satisfactory completion of primary endpoints, patients shall be transferred to DSU. At the DSU, in both groups, patients shall be given oral Oxycocet (combination of oxycodone and paracetamol) or Tylenol 3 (combination of codeine and paracetamol), as a PRN medication, if necessitated by the patient's pain. Nurses shall note down the occurrence of any pain and nausea necessitating treatment in the patient's CRF. Readiness to discharge home is noted down for each patient. The RA shall collect the CRFs from PACU and DSU and deposit safely in a locked filing cabinet.

Planned Outcomes: Our combined primary outcome will be proportion of patients with SAME, as compared between the 2 groups. Analgesia will be based on NAS 0-10 (appendix 3), and PONV will be based on VDS 0-5 (appendix 3). These observations will be made at the end of 2 hrs or before (corresponding to the time of discharge from PACU), by the PACU nurse, in the specified CRF. All the other outcomes to be recorded within the hospital, along with the time of their measurement and proposed analysis method are noted in table 1.

Sample Size Calculation: It was calculated based on the primary, binary outcome of proportion of patients with SAME, which will be compared using a chi-square test. According to literature,

Most Effective Opioid Analgesia in Ambulatory Surgeries: a randomized control, investigator blinded, parallel group with superiority design study of Morphine versus Hydromorphone
 [name], Principal Investigator SJHH
 [name], Principal Investigator HHS

approximately 30%-40% of patients are provided with inadequate analgesia after their AS,^(25, 26) with a similar number also known to suffer from PONV after AS.^(3, 24) Our chart reviews suggests that approximately 20% of patients suffer from inadequate analgesia with PONV using morphine. For a 2-sided test, with an alpha of 0.05 and a power of 90%, and with an estimated effect size of 10% (p1= 80% and p2= 90%), a sample size of 266 per group was calculated. However, for recruitment we shall have a target of 275 per group, for a total of 550 patients (rounding off). For the primary outcome analysis, we expect minimal loss through attrition as the study involves a follow up of few hours. The expected recruitment is approximately 20 cases per month at each of the 3 sites. We expect the trial to run for 10-12 months.

Table 1: Study Outcomes, and their Measurement and Analysis

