OUTCOME MEASURE	TYPE	MEASUREMENT	TIME OF MEASUREMENT	ANALYSIS METHOD
Primary outcome Satisfactory Analgesia with minimal PONV	Binary	NAS=<4/10 VDS<2/5	At 2hrs or at the time of discharge from PACU	Chi-square
Severe Itching	Binary	VAS>5/10	At 2hrs or at the time of discharge from PACU	Chi-square or Fisher's test (as appropriate)
Severe Sedation	Binary	Ramsey Score >3/6	At 2hrs or at the time of discharge from PACU	Chi-Square or Fisher's test (as appropriate)
Severe Respiratory Depression	Count	All cases needing treatment as counts	At 2hrs or at the time of discharge from PACU	Chi-square or Fisher's test (as appropriate)
Use of Ketorolac	Continuous	Total dose used per patients as a rescue therapy	At 2hrs or at the time of discharge from PACU	T test
Mean dose of Analgesic Used	Continuous	Dose of Analgesic used per patient in EMU	At the time of hospital discharge	T test

Most Effective Opioid Analgesia in Ambulatory Surgeries: a randomized control, investigator blinded, parallel group with superiority design study of Morphine versus Hydromorphone
 [name], Principal Investigator SJHH
 [name], Principal Investigator HHS

Patient Satisfaction-Mean score (0-10)	Continuous	Mean Score calculated between 0 to 5 scale	At the time of hospital discharge	T test
Time to discharge from PACU	Continuous	Mean time in hrs	At 2hrs or at the time of discharge from PACU	T test
Time to discharge from the hospital	Continuous	Mean time in hrs	At the time of hospital discharge	T test

Outcomes at Post-operative Day 1:

Patients will be approached by 1-2 phone calls shall be done during the next day; if unanswered, a repeat call will be made on the subsequent day (2nd day after discharge); for responders, the following questions will be asked.

1. What was your average pain score over the last 24 hrs, in 0-10 NAS scale, after you were discharged home?
2. After discharge, did you have nausea-severe enough to require medications at home?
3. After discharge, did you have vomiting-severe enough to require medications at home?
4. After discharged home, did you require a visit to ER, or readmission?

Outcomes at 3 months:

Patients will be contacted by a mailed package at 3 months after surgery to collect the following outcomes.

1	Do you have Persistent Pain (which started with or after surgery), at or near the surgical area?	Yes or No
2	Intensity of Pain	NAS: 0-10
3	Brief Pain Inventory-Interference Items 7 Items: each item scored between 0-10	

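### Sedation, itching and respiratory depression are not specified for recording after PACU exit, so later opioid harms can go uncounted, possibly unequally between arms

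*Combined protocol and SAP*

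**What the plan says.** - **Window.** In Table 1 the rows for severe itching, severe sedation and severe respiratory depression all carry the same time of measurement: "At 2hrs or at the time of discharge from PACU". Respiratory depression is defined there as "All cases needing treatment as counts". Under Planned Outcomes the protocol makes Table 1 the governing list: "All the other outcomes to be recorded within the hospital, along with the time of their measurement and proposed analysis method are noted in table".
- **When the window closes.** DSU Stay and Protocol: "At the end of 2 hours or after satisfactory completion of primary endpoints, patients shall be transferred to DSU". The primary endpoint consists of the NAS and VDS scores.
- **What happens next.** In the DSU, if pain requires it, "patients shall be given oral Oxycocet (combination of oxycodone and paracetamol) or Tylenol 3 (combination of codeine and paracetamol), as a PRN medication". The recording instruction there is "Nurses shall note down the occurrence of any pain and nausea necessitating treatment".
- **After discharge.** The day-1 call asks about average pain, nausea and vomiting needing medication, and an ER visit or readmission. The 3-month package covers persistent pain, its intensity and interference, global change and analgesic use.
- **Pharmacology.** The background section gives the half-life of transfer from plasma to effect site as follows: "transfer life from plasma to effect site) is 1.6hr – 4 hr for M, compared to 18-38 min for HM".
- **Objectives.** Severe itching, significant sedation and significant respiratory depression are tertiary objectives.

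**The concern.** The background section defines the clinical value of an opioid as satisfactory analgesia with limited side effects, and it names drowsiness, sedation, itching and respiratory depression among those side effects. The plan follows pain, nausea and vomiting to 24 h, but specifies the other opioid harms only to PACU exit. That is the point at which a second, oral opioid may be added.

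Three things follow.

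1. A late harm would enter none of the three safety rows.
2. Observation time varies between patients, and it varies between arms if one drug gets patients out of PACU sooner.
3. The two drugs reach the effect site at different speeds, so one clock time cuts them off at different stages. A difference in counted harms could then partly reflect timing.

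**Working it through.** **Step 1: is there a recording gap?** Setting the provisions side by side:

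| Period | Specified for recording | Sedation, itching, breathing? |
|---|---|---|
| PACU, up to 2 h or exit | Table 1 rows | Yes |
| DSU to hospital discharge | Pain and nausea needing treatment; readiness to go home; time to hospital discharge, analgesic dose and satisfaction (Table 1) | Not specified |
| Day-1 call | Pain, nausea, vomiting, ER visit or readmission | Only through ER visit or readmission, cause not asked |
| 3 months | Pain, interference, global change, analgesic use | No |

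I found no adverse-event section elsewhere in the text that fills the second and third rows.

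**Step 2: do the protocol's half-lives put the cut-off at different stages?** The inputs are 1.6-4 h = 96-240 min for morphine and 18-38 min for hydromorphone. Assume first-order transfer and a steady plasma level. The share of equilibration reached at time t after a dose is 1 − 2^(−t / half-life).

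- t = 120 min, morphine: 1 − 2^(−120/96) = 58% and 1 − 2^(−120/240) = 29%.
- t = 120 min, hydromorphone: 1 − 2^(−120/18) = 99% and 1 − 2^(−120/38) = 89%.
- t = 60 min (early exit, or a dose given 1 h before the window closes): morphine 16%-35%, hydromorphone 67%-90%.

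The ranges do not overlap at equal times.

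**Step 3: does that mean hydromorphone's harms fall inside the window and morphine's outside?** Equilibration is not harm observed, so allow the plasma level to fall. The documents give no plasma half-life, so the values below are assumptions. For a single bolus with elimination rate k and transfer rate ke (each ln 2 / half-life), the share of total effect-site exposure inside T minutes is

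k·ke/(ke − k) × [(1 − e^(−kT))/k − (1 − e^(−ke·T))/ke],

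and the peak is at ln(ke/k)/(ke − k). Example: plasma half-life 120 min, morphine transfer half-life 96 min, T = 120. Then k = 0.005776 and ke = 0.007220, and the share is 0.02888 × (86.56 − 80.27) = 18%.

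| Assumed plasma half-life | Exposure inside 2 h, morphine | Exposure inside 2 h, hydromorphone | Peak, morphine | Peak, hydromorphone |
|---|---|---|---|---|
| 2-4 h | 5%-18% | 18%-41% | 155-346 min | 58-120 min |
| 30-60 min | 14%-42% | 51%-86% | 73-160 min | 33-68 min |

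With 2-4 h, most exposure falls after 2 h in **both** arms. With 30-60 min, hydromorphone is mostly inside, but morphine's peak is then often inside too. Morphine lags in every case; how much depends on an input the documents do not give.

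**Step 4: can unequal exit times offset the lag?** Use the 2-4 h assumption and let hydromorphone patients leave at 60 min and morphine patients at 120 min. The same formula gives 6%-19% inside the window for hydromorphone and 5%-18% for morphine, which is practically equal.

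**Step 5: the plan's own figure.** No sample size is stated for the harm outcomes. The primary figure, from 80% against 90%, two-sided 0.05 and 90% power, is (1.960·√(2·0.85·0.15) + 1.2816·√(0.8·0.2 + 0.9·0.1))² / 0.10² = 265.9, that is 266 per group as stated. Nothing here changes it.

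**The case against.** The best defence is that a PACU window matches the place where the randomised drug is given. In the DSU, oral opioids are available in both arms, so later events are harder to attribute. These are tertiary outcomes, and Table 1 legitimately supplies the window that the objectives leave open, so there is no inconsistency between the two. All of this stands. It bears on how much weight the point gets, and it does not remove the gap.

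A reader might infer several stronger things that the documents do not support.

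- **That the comparison is biased in morphine's favour.** This is a pharmacokinetic inference. No harm rates or concentration-response figures are given, and Steps 3 and 4 show that both the contrast and its net direction depend on assumptions. The trial's hypothesis favours hydromorphone; if its patients meet the endpoints and leave sooner, their shorter observation works against the lag.
- **That no form captures these events.** The PACU and DSU pages of the CRF are not among those in Appendix 1, and the DSU text does not say that nurses record pain and nausea alone. What can be said is that the text specifies no such recording.
- **That a patient given naloxone in the DSU would appear in no outcome.** Time to hospital discharge would reflect any delay, and the day-1 call asks about ER visits and readmission. Neither gives the cause.
- **That the transfer rule contradicts the PACU sedation and respiration checks.** Those checks govern withholding doses, and the transfer rule governs moving the patient. No contradiction is shown.

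**Conclusion.** The recording gap is in the text and does not depend on any pharmacology: after PACU exit, at 2 h or earlier, sedation, itching and respiratory depression are not specified for recording. Observation time for these outcomes therefore varies between patients, and possibly between arms.

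A differential under-count, possibly larger in the morphine arm, is plausible from the protocol's own half-lives (29%-58% against 89%-99% equilibrated at 2 h, assuming a steady plasma level). Its size in events and its net direction cannot be computed from the documents.

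This is a cheap improvement to tertiary outcomes. The primary outcome and the 266 per group are unaffected.

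**What to change.** - **Table 1.** For severe itching, severe sedation and respiratory depression, set the time of measurement to any time from PACU entry to hospital discharge. Report each in total and split PACU / DSU. Table 1 already uses hospital discharge as the time point for three other outcomes, and the split keeps the PACU-only result available.
- **DSU Stay and Protocol.** Ask DSU nurses to record respiratory depression, naloxone use, sedation score and itching, with times, on the CRF they already complete.
- **Day-1 call.** Add one question on excessive drowsiness or breathing difficulty.

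The cost is a few CRF lines and one call question. The downside is that DSU events may be partly due to the oral opioids; the PACU / DSU split makes that visible.

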Hence, we will also look for any differences in pain, nausea and vomiting over the first 24 hrs after the surgery, along with chances of readmission or ER visits within the same period, post discharge. At 3 months, we will look for the incidence of persisting pain after surgery.

Hypothesis

In patients who undergo ambulatory surgical procedures causing at least moderate pain, hydromorphone (HM) increases the proportion of patients who would demonstrate 'satisfactory analgesia [$=<4/10$ NAS] with minimal or no postoperative nausea-vomiting (PONV) [$<2/5$ VDS] as compared to morphine (M), when both are administered intravenously, in equianalgesic doses, and are compared at 2 hours after surgery in PACU.

2. Specific Objectives

The primary objective of this study is to compare the proportion of patients with SAME (satisfactory analgesia and minimal emesis) after AS, when using M compared with HM, during the immediate postoperative hospital stay.

Secondary objectives include:

1. Total dose of analgesic used in PACU, in morphine equivalents,
2. Time to discharge or readiness to discharge from the DSU,
3. Proportion of pain, and its comparison after discharge, within 24 hours,
4. Proportion of nausea, and its comparison after discharge, within 24 hours,
5. Proportion of vomiting, and its comparison after discharge, within 24 hours,
6. Incidence of CPSP at 3 months after discharge

The tertiary objectives include:

1. Proportion of patients with severe itching,

Protocol Version Date: Version 5 / June 23, 2015

Most Effective Opioid Analgesia in Ambulatory Surgeries: a randomized control, investigator blinded, parallel group with superiority design study of Morphine versus Hydromorphone

[name], Principal Investigator SJHH

[name], Principal Investigator HHS

2. Proportion of patients with significant sedation,
3. Proportion of patients with significant respiratory depression,
4. Patient satisfaction score at the time of discharge,
5. Time to discharge or readiness to discharge from the PACU,
6. Use of ketorolac as a rescue medication,

METHODS

The study is designed as a multisite, 2 arm, parallel, superiority design with randomization of patients and blinding of patients, health care providers (physicians and nurses) and research personnel (research coordinator and data analyst). Patients will be stratified based on site and laparoscopic/open surgeries. Intention to treat approach will be used for design and analysis.

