PACU Stay: The actual study intervention (hence randomization) will only become applicable once the patient is moved to the PACU. Every patient will be treated as per the protocol during the intraoperative management, which primarily restricts the use of any study opioids. The details are provided in appendix 2. The nurse looking after the study patient in PACU will administer the medication as per the study protocol. This would include analgesia with equipotent doses of M or HM administered in titrated doses. Syringes will be pre-prepared from the pharmacy in EMUs; 1ml=1mg of morphine or 0.2 mg of hydromorphone. We shall consider a potency ratio of 1:5 (M: HM), considered equivalent in literature.⁽⁹⁾ Analgesia will be provided according to the following guideline. A similar method has been advised to be safe and effective for titrated analgesia in PACU.⁽²⁴⁾ Readiness to discharge from PACU and outcomes are noted at 2 hrs, or at the time of discharge to DSU.

Most Effective Opioid Analgesia in Ambulatory Surgeries: a randomized control, investigator blinded, parallel group with superiority design study of Morphine versus Hydromorphone
[name], Principal Investigator SJHH
[name], Principal Investigator HHS

PACU Protocol (titrate the opioid medication to achieve desired pain score)

- Patient to be asked for their pain score, and if it is more than 4 out of 10 (NAS): to receive the 1st dose within 5 minutes after coming to PACU: 0.04mg/kg morphine units (rounding off to the nearest 1 ml or 0.5 ml); with a maximum of 3 mg of morphine equivalents.
- Repeat doses: 0.02 mg/kg morphine units every 5-10 minutes to titrate for analgesia and side effects (rounding off to the nearest 1 ml or 0.5 ml)
- If no side effects observed-titrate to have analgesia: NAS =<4/10.
- If Nausea-Vomiting observed: record it in the CRF provided and treat it with antiemetics (Ondansetron 1-4 mg IV, Dimenhydrinate 25-50 mg)
- If patient is too sedated (<3-Ramsey Sedation Scale)-withhold the next dose and restart the bolus if the score is >3
- If respiratory depression present, withhold the next dose, treat with Naloxone if necessary.
- Ketorolac IV 15-30 mg as rescue medication if patient does not tolerate the study opioid or if the patient does not satisfy the success of satisfactory analgesia at more than 1 hr.

DSU Stay and Protocol:

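### Severe sedation and severe itching are scored on one reading at PACU exit, so episodes that arose earlier in PACU and settled are not counted

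*Combined protocol and SAP*

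**What the plan says.** Table 1 lists severe itching (a VAS above 5 out of 10) and severe sedation ("Ramsey Score >3/6") as binary outcomes. The time of measurement for each is "At 2hrs or at the time of discharge from PACU". The PACU Stay section gives the same rule: "Readiness to discharge from PACU and outcomes are noted at 2 hrs, or at the time of discharge to DSU". The Planned Outcomes paragraph makes Table 1 the governing source on timing: "All the other outcomes to be recorded within the hospital, along with the time of their measurement and proposed analysis method are noted in table" (the reference is to Table 1).

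Exit from PACU is not at a fixed time. Under DSU Stay and Protocol, "At the end of 2 hours or after satisfactory completion of primary endpoints, patients shall be transferred to DSU".

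During titration the PACU Protocol uses sedation to control dosing: "If patient is too sedated (<3-Ramsey Sedation Scale)-withhold the next dose and restart the bolus if the score is >3". It does not say that these sedation scores are to be written down. For nausea and vomiting, by contrast, it does call for a CRF entry when they are observed.

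The tertiary objectives include "Proportion of patients with significant sedation" and the corresponding proportion for severe itching.

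**The concern.** The Introduction argues that opioids should be compared on satisfactory analgesia together with limited side effects, and it names sedation and itching among those side effects. A reading at exit answers a narrower question: who is still sedated or itching on leaving PACU. It does not show who was affected while the study drug was being titrated.

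For sedation, the protocol's own dosing rule acts on the event before it is measured. A patient whose next dose was withheld for over-sedation and who recovered before transfer is recorded according to the recovered score. The episode that best separates two opioids on tolerability can therefore drop out of the comparison. The reading is also taken earlier in patients who reach the primary endpoint early, so the observation point varies between patients.

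**Working it through.** **1. The plan's own figure.** Inputs from Sample Size Calculation: 80% against 90%, two-sided alpha 0.05, power 90%. With pooled variance and no continuity correction,

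n = [1.960·√(2·p̄(1−p̄)) + 1.2816·√(p1(1−p1)+p2(1−p2))]² / (p1−p2)², where p̄ = 0.85.

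n = [1.960·√0.255 + 1.2816·√(0.16+0.09)]² / 0.01 = [0.9897 + 0.6408]² / 0.01 = 265.9, so 266 per group.

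This matches the stated 266. It concerns the primary outcome only and does not depend on how sedation or itching is timed. No sample size or power is stated for those two outcomes.

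**2. Is the measurement a single reading?** Several rows of Table 1 share the same timing cell, so the measurement column has to decide.

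| Row | Measurement | Covers the whole PACU stay? |
|---|---|---|
| Ketorolac | total rescue dose per patient | yes, a cumulative total |
| Respiratory depression | all cases that needed treatment | yes, counts every such case |
| Severe sedation | score threshold | no look-back wording |
| Severe itching | score threshold | no look-back wording |

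Where the plan counts over the stay, the measurement cell says so. The sedation and itching cells do not, and the PACU Stay section says outcomes are noted at 2 hours or on transfer. The DSU section asks nurses to note pain and nausea that need treatment, but not sedation or itching.

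**3. What the loss could cost.** The documents give no sedation or itching rates, so the following are assumptions: any-time rates of 15% and 7%; 275 per arm (the recruitment target); and the same share s of events still present at exit in each arm. For sedation, the illustration also assumes that the scale conflict in step 4 has been settled. The rates seen at exit are then p1 = 0.15s and p2 = 0.07s, and

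power = Φ{ [(p1−p2) − 1.960·√(2p̄(1−p̄)/275)] / √([p1(1−p1)+p2(1−p2)]/275) }.

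Worked for s = 1: p̄ = 0.11; the two standard errors are 0.02668 and 0.02646; (0.08 − 1.960×0.02668)/0.02646 = 1.05; Φ(1.05) = 85%.

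| Share persisting to exit | Rates at exit | Expected events per arm | Power |
|---|---|---|---|
| 100% | 15.0% vs 7.0% | 41 vs 19 | 85% |
| 50% | 7.5% vs 3.5% | 21 vs 10 | 54% |
| 30% | 4.5% vs 2.1% | 12 vs 6 | 35% |
| 20% | 3.0% vs 1.4% | 8 vs 4 | 25% |
| 10% | 1.5% vs 0.7% | 4 vs 2 | 14% |

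The pattern does not hinge on that pair of rates. At persistence of 100%, 50%, 25% and 10%, assumed rates of 20% and 10% give 91%, 61%, 34% and 16%; assumed rates of 10% and 5% give 61%, 34%, 19% and 10%.

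**4. Direction of the sedation scale.** Three places disagree.
- PACU Protocol: a score below 3 is too sedated, and dosing restarts above 3.
- Table 1: a score above 3 is severe sedation.
- Appendix 3: 0 is no response to a test stimulus, 5 is a ready response to the patient's name and 6 is agitated, so higher scores mean more alert.

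Read literally, an alert patient scoring 5 counts as severely sedated and a patient scoring 1 does not. Until this is reconciled, a worst sedation score has no defined direction.

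**The case against.** The strongest reply is that the timing column may say when data are collected, not over what period they apply. Ketorolac and time to PACU discharge share the cell and plainly describe the whole stay. The PACU page of the CRF is not among the forms in Appendix 1 as supplied, so look-back wording on it cannot be excluded. This stands as a reason for caution about the word only. It does not remove the point: the measurement cells for sedation and itching contain just a threshold, and no section asks for a worst or any-time value.

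Sedation and itching are also tertiary. The hypothesis expresses side effects through PONV, which is part of the primary outcome; nausea and vomiting are recorded when observed, and treated respiratory depression is counted in full. That stands, and it limits the importance of the point.

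Itching is the weaker half. The PACU Protocol names no itch-specific dose hold or treatment, only general titration to side effects, so nothing documented shows that severe itching would have settled by exit.

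A reader might infer that exit readings will be close to zero in both arms because patients are fit to leave by then. The documents do not support this. Sedation and itching are not stated criteria for transfer, which is tied to 2 hours or to the pain and PONV endpoint. Under the sedation cut-off as written, the recorded rate at exit could be high, because alert patients score above 3.

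A reader might also infer that the trial would show the two drugs to be equally safe. It would not: a non-significant difference on a tertiary outcome in a superiority trial does not establish equivalence.

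**Conclusion.** The point holds as a limited but worthwhile improvement to two tertiary endpoints. As written, Table 1 counts severe sedation and severe itching from one reading at PACU exit and misses episodes that settled beforehand. For sedation this follows from the text, since the dosing rule acts on over-sedation before the reading is taken. For itching it is a reasonable expectation without documentary support.

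The primary analysis and the 266 per group are untouched. The loss in the side-effect comparison cannot be sized from the documents. The fall in power from 85% to between 54% and 14% rests wholly on assumed rates of 15% and 7%, persistence of 50% down to 10%, and equal persistence in the two arms. If persistence differed between the drugs, the exit comparison would also be distorted, in a direction the documents cannot settle.

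**What to change.** In Table 1, define severe sedation and severe itching as the worst score at any time from the first study dose to PACU exit. Add a worst-value-in-PACU field to the CRF for each. Keep the exit value as a descriptive measure.

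In the same edit, reconcile the direction and cut-off of the sedation scale across the PACU Protocol, Table 1 and Appendix 3, so that worst has one meaning. The sponsor must decide which passage governs.

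The cost is a wording change in Table 1, two CRF fields, the reconciliation of the sedation scale and slightly more nurse recording. The extra recording is mainly for itching, since sedation is already assessed to guide dosing. The change needs to be made before enrolment, because transient episodes that are not recorded at the time cannot be reliably recovered later.

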4	Global Impression of Change	Likert scale 1-7

Most Effective Opioid Analgesia in Ambulatory Surgeries: a randomized control, investigator blinded, parallel group with superiority design study of Morphine versus Hydromorphone
[name], Principal Investigator SJHH
[name], Principal Investigator HHS

5	Analgesic Use: Did you have to use any pain medications for more than 1 month, to help with pain, which started with or after Surgery?	Yes or No
---	---	-----------

Statistical Analysis: The study will be analyzed using an intention to treat approach. The individual outcomes along with their respective analyses method have been listed within the table 1. Broadly the dichotomous outcomes will be reported as proportions and analyzed using a chi-square test to detect a significant difference ($p<0.05$). Precision will be reported using 95% CI. Continuous outcomes will be analyzed using an unpaired 2-tailed student t test for significance ($p<0.05$). Means and standard deviations shall be reported along with 95% CI. We also plan to perform logistic multivariable regression analysis to account for the influence of baseline covariates, which are listed in appendix 1. A sensitivity analysis will be performed to compare the effects of laparoscopic surgeries vs open surgeries.

Trial Management: This trial will be conducted at 3 hospital sites affiliated with McMaster University, Hamilton: St Joseph's Hospital, McMaster University Hospital and Juravinski Hospital.

Data Management and Quality Control: All study data including CRFs of each patient, shall be securely stored at the central office. A summary table indicating study timeline from enrollment to final follow-up (<http://www.spirit-statement.org/title/>) shall be included for each patient.⁽²⁷⁾ CRF's will be collected as paper forms. They shall be periodically cross-checked for completeness and entered into a suitable electronic master file. All reports of incorrect randomizations, protocol violations or incomplete data shall be noted.

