APPENDIX 3: Outcome Measurement Scales

1. Numerical Analogue Scale for Pain (NAS)

2. Verbal Descriptive Scale for PONV: the presence and severity of PONV (reference 9)

0	no nausea
1	mild nausea
2	moderate nausea-may need treatment
3	frequent vomiting –controlled with antiemetics
4	severe vomiting-uncontrolled with antiemetics.

3. Severity of Respiratory Depression: Presence of one or both of the following

- presence of Respiratory Rate below 10
- Presence of Oxygen saturation <90\

4. Ramsay Sedation Scale

Response to verbal command	Numerical Score
Agitated	6
Responds readily to name spoken in a normal tone	5
Lethargic response to name spoken in normal tone	4
Responds only after name is called loudly and/or repeatedly	3
Responds only after mild prodding or shaking	2
Does not respond to mild prodding or shaking	1
Does not respond to test stimulus	0

Most Effective Opioid Analgesia in Ambulatory Surgeries: a randomized control, investigator blinded, parallel group with superiority design study of Morphine versus Hydromorphone
[name], Principal Investigator SJHH
[name], Principal Investigator HHS

5. Patient Satisfaction Score and Severity of Itching: Visual Analogue Scale

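### The Table 1 cut-off for severe sedation points the wrong way: on the protocol's own scale it counts the less sedated patients as events

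*Combined protocol and SAP*

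**What the plan says.** Sedation is tertiary objective 2 under Specific Objectives: "Proportion of patients with significant sedation". No cut-off is given there. The Statistical Analysis section refers the reader elsewhere for definitions and methods: "The individual outcomes along with their respective analyses method have been listed within the table 1". In Table 1 the row for severe sedation is binary, measured at two hours or on leaving the PACU, compared by chi-square or Fisher's test, and defined as "Ramsey Score >3/6". That cell is the only definition of the endpoint.

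The scale is printed once, in Appendix 3, item 4. Score 6 is agitated. Score 5 is "Responds readily to name spoken in a normal tone", score 4 is "Lethargic response to name spoken in normal tone" and score 3 is "Responds only after name is called loudly and/or repeatedly". Scores 2 and 1 describe progressively weaker response to physical stimulation, and score 0 is "Does not respond to test stimulus".

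The PACU Protocol uses the scale at the bedside: "If patient is too sedated (<3-Ramsey Sedation Scale)-withhold the next dose and restart the bolus if the score is >3".

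**The concern.** Table 1 and Appendix 3 run in opposite directions. A patient who answers readily would be recorded as severely sedated, and one who cannot be roused would not. The condition that Table 1 calls severe sedation, a score above 3, is the same condition that lets the PACU nurse resume opioid boluses.

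The protocol's introduction lists sedation among opioid side effects and judges an opioid by adequate pain relief together with limited side effects. A sedation result reported with the wrong sign would credit the more sedating drug with the better profile. The outcome is tertiary, so this would mislead the safety comparison without touching the main conclusion.

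**Working it through.** **The plan's own figure.** The plan gives no expected rate or power for sedation. Its one calculated figure is the sample size for the primary outcome: 80% v 90%, two-sided alpha 0.05, power 90%. With pooled variance under the null,

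n = [1.96·√(2·0.85·0.15) + 1.2816·√(0.8·0.2 + 0.9·0.1)]² / 0.10² = (0.990 + 0.641)² / 0.01 ≈ 266 per group.

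This matches the plan and does not depend on the sedation cut-off.

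**Apply each cut-off to the Appendix 3 scores.**

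| Rule | Scores selected |
|---|---|
| Table 1 event, >3 | 4, 5, 6 |
| Complement, ≤3 | 0, 1, 2, 3 |
| PACU too sedated, <3 | 0, 1, 2 |

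The first two sets do not overlap and together cover the scale. The three deepest levels (0 to 2) are all non-events under Table 1.

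**Effect on the difference between arms.** For each arm let a = P(score <3), b = P(score = 3) and c = P(score >3) = 1 − a − b. Then

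c_M − c_HM = −[(a_M − a_HM) + (b_M − b_HM)].

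This is exactly minus the ≤3 difference, whatever the rates. When morphine truly has more patients below 3, the Table 1 difference has the opposite sign to the <3 difference if and only if b_HM − b_M < a_M − a_HM.

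**Size of the error in level.** If a share q scores ≤3, Table 1 reports 1 − q. For assumed q of 1%, 2%, 5% and 10%, it reports 99%, 98%, 95% and 90%.

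**Scenarios.** Assume 5% of morphine and 2% of hydromorphone patients score <3, a true difference of +3 points (all entries morphine v hydromorphone):

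| Score exactly 3 | ≤3 | Table 1 (>3) | Table 1 difference |
|---|---|---|---|
| 0% v 0% | 5% v 2% | 95% v 98% | −3 |
| 5% v 5% | 10% v 7% | 90% v 93% | −3 |
| 20% v 20% | 25% v 22% | 75% v 78% | −3 |
| 2% v 5% | 7% v 7% | 93% v 93% | 0 |
| 2% v 8% | 7% v 10% | 93% v 90% | +3 |

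In the last row the sign agrees with <3 but is still reversed against ≤3. The threshold is a 3-point excess of score-3 patients on hydromorphone.

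**Effect on the test.** Take assumed counts of 14/275 v 6/275 at ≤3, using the recruitment target of 275 per group. The rates are 5.1% v 2.2%, a difference of +2.9 points. The standard error is √(0.0509·0.9491/275 + 0.0218·0.9782/275) = 0.0159, so the 95% CI is −0.2 to 6.0 points. Under Table 1 the same patients give 261/275 v 269/275, or 94.9% v 97.8%: a difference of −2.9 points, CI −6.0 to 0.2. Chi-square is 3.32 with p = 0.068 both ways.

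**Sampling variation.** In 200,000 simulated trials of 275 per arm with equal score-3 shares, the observed Table 1 difference had the opposite sign to the observed <3 difference in these proportions:

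- 5% v 2% scoring <3: 98.6%, 92.9%, 87.9%, 83.0% and 77.6% of trials, for score-3 shares of 0%, 2%, 5%, 10% and 20%.
- 2% v 1%: 91% down to 56% as the score-3 share goes from 0% to 20%.
- 1% v 0.5%: 83% down to 47%.

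Ties in the <3 counts explain part of the fall at the lower rates (about 9% of trials at 2% v 1%, 17% at 1% v 0.5%).

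**The case against.** The best defence concerns consequence; the text itself is plainly inconsistent.

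- *The test does not change.* Complementing a binary endpoint leaves the two-sided chi-square and Fisher p-values as they were. This stands against ≤3; against <3 the test can differ. It does not rescue the outcome, because the plan also reports proportions with 95% confidence intervals, and those would be wrong in level and sign.
- *Somebody would notice.* Severe sedation in 75% to 98% of patients leaving a PACU would prompt a look at Appendix 3. Probably so, and this lowers the practical risk. But the cut-off would then be chosen with the data in view, and the documents do not settle whether it should be <3 or ≤3.
- *Score 4 is lethargic, so the event set does contain some sedated patients.* True, but the set also contains scores 5 and 6 and leaves out everyone at 0 to 3.
- *The simulated reversal rates depend on assumed inputs.* This stands: they fall as the assumed rates fall. Low rates are plausible because dosing is withheld below 3 and the score is taken late in the PACU stay. The complement identity carries the argument without them.

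**Conclusion.** The point holds. Two parts of the protocol, Appendix 3 and the PACU rule, agree that low scores mean sedation. Table 1 contradicts both, and nothing recodes the score. Followed as written, the endpoint is the complement of score ≤3. The difference between arms is then exactly reversed against ≤3, with no assumption about rates. It is also reversed against <3 unless hydromorphone has enough extra patients at exactly 3 to offset the true difference (3 points or more in the 5% v 2% illustration). The error in level is large: at the assumed rates, Table 1 reports 75% to 98% where the true share below 3 is 2% to 5%.

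The damage is limited to one tertiary outcome. The primary outcome, the sample size of 266 and the direction of the bedside dosing rule are unaffected. It should be corrected, and it does not threaten the trial.

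**What to change.** Before analysis, change the Table 1 event to score <3, which matches the PACU rule, or to ≤3 if a patient who responds only to loud or repeated calling is meant to count. Choose one and state it. Use one label throughout, since the objective says significant and Table 1 says severe. Record the raw 0–6 score on the case record form with the direction of the scale printed beside it, so that either cut-off can be derived.

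As a separate matter, the PACU rule withholds below 3 and restarts above 3, so a score of exactly 3 is assigned to neither; one added clause settles it.

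The cost is one table cell, one clause and a note on the form. No new data are needed if the raw score is recorded.
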